## **Midpoint Visit b:**

- LP
- MRI

## **End-of-study Visit a:**

- Interim history review
- Medication review
- Adverse event review
- Confirm continued eligibility

Date: 04NOV2019

Protocol: v07

- Vital signs, height & weight
- Physical and neurologic exams
- Cognitive testing/Questionnaires
  - Clinical Dementia Rating (CDR)
  - Neuropsychiatric Inventory (NPI)
  - Activities of Daily Living (FAQ)
- PET scan (florbetapir)
- MRI
- EEG
  - o Flicker entrainment with exposure titration
  - o EEG evaluation and induced activity
- Eye tracking task
- Turn in journal/equipment if Flicker completed during second 4-week period

## **End of Study Visit b:**

- Retinal Imaging
- Lumbar puncture

**8.5 Assessments:** MCI will be assessed using raters blinded to the study design. The cognitive battery will consist of: MoCA, CDR-SB and the Geriatric Depression Scale to help determine subject eligibility.

## 8.6 Safety Measurements:

- a. Vital Signs Systolic blood pressure (SBP), diastolic blood pressure (DBP) and heart rate (HR) will be measured while the patient is in sitting position after five minutes rest at each office visit.
- b. Physical Exam A physician will perform a physical exam on all MCI patients at the screening visit to evaluate for any significant medical conditions. Subsequent physical exams will be performed by an MD or Nurse Practitioner.

#### 8.6.2 Other Assessments:

- a. Demographic Data Demographic data (gender, date of birth, marital status, ethnicity, race) will be collected for all patients.
- b. Concomitant Medication All meds taken by subjects as part of their routine health care will be documented during the study.

## 8.7 Participant Retention

Subjects who are enrolled in the study will be reimbursed for their time. Total study payment includes reimbursement for undergoing procedures and travel to the clinic for inperson study visits. Study partners who are required to accompany participants to their visits as well as monitor at home Flicker exposure sessions will also be reimbursed for their time.

Reimbursement will be made at the completion of the study. Emory University is required to complete form 1099 for any participant payments over \$600 in a year. To comply with

this federal mandate the researchers are required to obtain subject's social security number to complete the form.

## 8.8 Schedule of Assessments

On the following pages, the schedule of assessments for both treatment groups is presented.

Table 1. Schedule of Assessments for the Non-Exposure Phase/Flicker Exposure Phase

Visit Number	1a	1b	2a	2b	3	4	5	6a 	6b	7	8	9	10	11a 	11b
Study Week	Screening 		Baseline 		1	2	3	44	44	5	6	7	8	94	94
Consent	X														
Confirm eligibility	X			X											
Medical history and medication review	X							X						X	
Physical exam and neurological exam	X			X				X						X	
Vital signs + height + weight	X			X											
Sensory function (see/hear)	X							X							
APOE genotyping		X													
Blood for biomarkers		X							X						X
Cognitive assessments	X			X				X						X	
Retinal imaging		X							X						X
MR imaging	$X^5$		$X^5$					$X^3$	$X^3$					X	
Lumbar puncture		X							X						X
PET Scan			X					X						X	
Eye tracking				X				X						X	
EEG evaluation and induced activity	$X^6$			X				X						X	
Tolerance Testing	X							X						X	
Randomization/Study crossover				X				X							
Therapy training									X						
In-home observation visit										X					
In-home therapy										X	X	X	X		
Telephone call / email contact					X	X	X			X	X	X	X		X
Remote adherence monitoring										X	X	X	X		
Assessment of adverse events				X	X	X	X	X		X	X	X	X	X	

<sup>1Crossover visit (2-day visit) End of treatment visit (2-day visit)

<sup>3MRI will occur on either study visit 6a or 6b

<sup>4Study visits may extend over several days, depending on scheduling constraints

<sup>5MRI will be done at visit 1a if not done within the past 2 yrs or at 2a if done within the past 6 months

<sup>6Screening EEG may be repeated if entrainment criteria are not met or data are unreliable in subjects who have met all other eligibility criteria.

Table 2. Schedule of Assessments for the Flicker Exposure/Flicker Exposure Phase

Visit Number	la .	1b	2a	2b	3	4	5	6	7a 	7b	8	9	10	$11a^2$	11b
Study Week	Screening 		Baseline 		1	2	3	4	5 	5 	6	7	8	94	94
Consent	X														
Confirm eligibility	X			X											
Medical history and medication review	X								X					X	
Physical exam and neurological exam	X			X					X					X	
Vital signs + height + weight	X			X											
Sensory function (see/hear)	X								X						
APOE genotyping		X													
Blood for biomarkers		X								X					X
Cognitive assessments	X			X					X					X	
Retinal imaging		X								X					X
MR imaging	X 		X 						$X^3$	$X^3$				X	
Lumbar puncture		X								X					X
PET Scan			X						X					X	
Eye tracking				X					X					X	
EEG evaluation and induced activity	$X^6$			X					X					X	
Tolerance testing	X			X					X					X	
Randomization				X											
Therapy training				X											
In-home observation visit					X										
In-home therapy					X	X	X	X	X	X	X	X	X		X
Telephone call / email contact					X	X	X	X			X	X	X		
Remote adherence monitoring					X	X	X	X	X	X	X	X	X		
Assessment of adverse events				X	X	X	X	X	X		X	X	X	X	

<sup>1Midpoint clinic visit (2-day visit)

<sup>2End of treatment visit (2-day visit)

<sup>3MRI will occur on either study visit 7a or 7b

<sup>4Study visits may extend over several days, depending on scheduling constraints

<sup>5MRI will be done at visit 1a if not done within the past 2 yrs or at 2a if done within the past 6 months

<sup>6Screening EEG may be repeated if entrainment criteria are not met or data are unreliable in subjects who have met all other eligibility criteria.

## 9. DATA RECORDING, RETENTION, AND MONITORING

## 9.1 Electronic Case Report Forms

Electronic Case Report Forms will be completed for each patient who signs Informed Consent. All clinical information requested in this protocol will be recorded on the eCRFs. If an error is made on documents collected (source documents), a single line will be drawn through the error and the correct response will be written adjacent to the error; the change will be initialed and dated.

## 9.2 Retention and Availability Of Records

The Investigator will make study data accessible to Regulatory Agency inspectors upon request. A file for each patient will be maintained that includes the signed ICF and the Investigator's copies of all source documentation related to that patient. The Investigator will ensure the reliability and availability of source documents from which the information on the CRF was derived.

Study documentation will be maintained, including documents created or modified in electronic format, for at least 15 years following the completion of the study. ICFs, and adequate records for the receipt and disposition of all study drugs will be retained for a period of 2 years following the Food and Drug Administration (FDA) or other regulatory approval date of the drug or until 2 years after the drug investigational program is discontinued, unless a longer period is required by applicable law or regulation.

#### 10. ASSAY MEASURES AND ANALYSES

**10.1Genotyping** for apolipoprotein E4 allele status will be performed in the Emory Genetics Core facility. Apolipoprotein E4 allele status will not be disclosed to study participants.

**10.2 EEG.** We will measure electrical brain activity using EEG from the scalp. For the EEG recording session, a cap (similar to a swim cap) will be placed on the participant's head and electrodes attached. Gel will be placed on the hair/head so that the electrodes can get a good connection to detect electrical charges that come from brain activity. This gel is easily removed with hair washing.

During the EEG study session, you will be seated in a chair. You will be asked to rest quietly with your eyes open. EEG will be recorded before, during and after use of the Flicker device (Figure 3). When the Flicker device is not in place, participants may be asked to perform simple movements, to perform a computer/iPad-based task with button presses, and/or to complete mood and cognitive assessment questionnaires.

19

Protocol: v07

There are no known risks of EEG. The gel in the hair can be sticky but is easily removed with shampooing. The EEG session may last up to 3 hours total time (including electrode placement and recording time) and will occur at 3 time points during the study: baseline, midpoint, and end-of-study.

EEG evaluation will be performed at Visits 1a and 2b for both groups to determine whether it is possible to entrain the gamma waves. If subjects' brain waves are unable to become entrained, they will be removed from the study. Screening EEG may be repeated if entrainment criteria are not met or data are unreliable in subjects who have met all other eligibility criteria.

**10.3 Lumbar Puncture (LP):** Lumbar puncture will be performed by a qualified clinician trained to perform the procedure. 20ml of CSF is collected using sterile technique and will be assayed for both known and novel biomarkers of disease, including inflammatory markers. Lumbar punctures will occur at the three in-person clinic visits (screening, midpoint, and end of study).

**10.4 CSF and Serum Biomarkers.** AD biomarkers including Aß42, tau, and phospho-tau levels in the CSF will be assayed at baseline, midpoint, and end of study visits. Specialty assays for inflammatory markers will also be conducted via a commercial vendor with specialized panels for measuring these markers (OLink, Sweden). Results are not disclosed to participants.

**10.5 MRI.** Brain MRI will be obtained or reviewed at screening to verify eligibility, at screening or baseline, at midpoint and end of study.

MRI films performed clinically within the past two years will be reviewed by the investigators for eligibility in the study. If a subject does not have clinical MRI films available, the MRI will be performed and reviewed prior to performance of the LP for safety reasons and to ensure that the subject meets eligibility criteria.

The 3T MR acquisition sequences will include all, or a subset of, the following 1) Structural MRI, 2) FLAIR,3) T2\*GRE; 4) arterial spin labeling (ASL), and 5) resting state connectivity. MRI measurements of brain structure have been show to demonstrate brain atrophy (which correlates with neuron loss) in MCI and AD and increasing rates of brain atrophy as subjects become more impaired. Therefore, structural MRI is used as a measure of the rate of disease progression in AD treatment trials. Structural MRI (MPRAGE//IRSPGR) data will be used both as the rate of change as well as a predictor of future change. Cerebrovascular disease (especially white matter lesions (WMLs) will be assessed with FLAIR. Cerebral blood flow, which closely correlates with cerebral hypometabolism as an early biomarker of AD pathogenesis, will be measured by ASL imaging. Finally, resting state fMRI will be used to determine functional connectivity changes.

All MRIs will be reviewed by the investigators and the investigator will determine and document any clinically significant findings.

**10.6 PET Scan.** The PET scan includes injection of florbetapir (10 mCi [+/- 10%]) administered by intravenous bolus injection. During the 50-minute uptake phase, participants will wait in a quiet room. The PET scan will begin at approximately 50 minutes post-florbetapir injection. Brain images will be acquired continuously for a period of 20-40 minutes (scan time based on scan quality and the need for repeat sequences).

**10.7 Cognitive testing.** Cognitive testing will occur at the baseline visit for each participant. A series of pen and paper or computer-based tests are administered to assess the current cognitive status (tests listed under Baseline visit 2b). At visit 1a, only the MoCA will be administered to determine eligibility.

10.8 Study questionnaires. Interviews will be conducted at each of the three time points in the study: baseline, midpoint, and at end-of-study. These questionnaires are conducted with the study partner and are meant to assess subjective impressions of the participant's current behaviors and level of function. One questionnaire (the Clinical Dementia Rating [CDR]) also asks questions of the participant and helps to offer insight into their current beliefs about their cognitive status.

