## 2. SPECIFIC AIMS

- **2.1**Aim 1. Assess the safety, and tolerability of gamma flicker and subject compliance. We will determine in 10 subjects with a diagnosis of MCI whether flicker exposure for 1 hour every day is well tolerated and whether subjects comply with the study procedures. In addition, we will closely monitor the safety of this procedure and document the occurrence of any adverse events.
- **2.2**Aim 2. Assess effects of driving gamma on blood flow in patients with MCI. Blood flow decreases very early in Alzheimer's disease and this decrease is thought to lead to amyloid build up and functional deficits. We will determine if gamma flicker increases blood flow in Alzheimer's patients. We will perform these tests in approximately 10 patients with mild cognitive impairment (MCI) in collaboration with Dr.'s [name] and [name] and the Emory BHC/ADRC. These pilot studies will support our application for an NIH grant to test gamma flicker in Alzheimer's patients in a clinical trial.
- 2.3 Aim 3. Assess effects of driving gamma on amyloid beta levels and inflammation markers in patients with MCI. We will assess amyloid beta levels in the brain (florbetapir PET), cerebral spinal fluid (Aß42 Luminex assay), the current gold standards in the field, and in the retina (Neurovision), a new approach currently being validated at the Emory Brain Health Center. We will also assess inflammatory markers in the cerebral spinal fluid (OLink inflammatory panel). We will perform these tests in 10 patients with mild cognitive impairment (MCI), as determined by clinical or research assessment using local standards at the Emory Brain Health Center (BHC)/ Alzheimer's Disease Research Center (ADRC).

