## 4. EXPERIMENTAL DESIGN AND METHODS

4.1 Overview: For this 9-week study, 10 subjects with mild cognitive impairment (amnestic or multi-domain subtypes) will be randomly assigned to two study arms. Although all participants will receive Flicker exposure, half of the participants will receive the exposure (driving gamma) during the entire study period (8 weeks of Flicker) while the other half of the participants will receive Flicker exposure for half of the study period (2nd 4-weeks). During the 9-week course of the study, participants will undergo venous blood draws and lumbar puncture for biomarker analyses at baseline, midpoint and at 9 weeks. At the study week 4 time point, the participants currently undergoing Flicker exposure will continue with their sessions while at week 4, those initially randomized to non-exposure will initiate Flicker exposure. The primary goals are to measure safety and FLICKER tolerance while verifying the intended response. Secondary objectives include monitoring possible effects of Flicker exposure on clinical findings and biomarkers of AD progression, including CSF amyloid, tau, and phospho-tau, and volumetric MRI, as well as PET (florbetapir) and arterial spin labeling MRI and retinal amyloid changes.

**4.2 Sample Size and Power.** This is a pilot study designed to assess feasibility and tolerability in the patient population. Although the sample size of 10 subjects will allow us to make certain claims about tolerability, we do not anticipate generating clinically meaningful,

broadly applicable results from this data. Thus, our sample size is driven by the need to collect pilot data that will position us to develop a clinical trial, if warranted, based on the technology described here.

- **4.3 Flicker tolerance to date.** For studies conducted to date by Cognito Therapeutics, a total of 17 participants have undergone daily periods of sensory stimulation for up to one hour (the study paradigm planned for this work). These subjects include young adults, older adults, and older adults with cognitive impairments. These studies have helped establish the feasibility of sensory stimulation with regards to safety, comfort, and tolerability of the exposure in patients with mild-to-moderate cognitive impairments. No device or exposure-related adverse events have been reported during this study.

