## 8.2 Screening Visits. Screening Visit 1a:

- Subjects will sign a written informed consent prior to any study-related procedures.
- Medical history, including review of medications
- Physical and neurologic exams
- Vital signs, including: blood pressure, heart rate, respiratory rate, temperature
- Height and weight
- Sensory function (see/hear)
- Cognitive Testing Montreal Cognitive Assessment (MoCA)
- Flicker Tolerance Testing
- EEG
  - Flicker entrainment and exposure titration
- MR Imaging
  - If imaging is available within 6 months of screening visit 1a (including an arterial spin labeling [ASL] sequence), the screening MRI may not be performed

Screening visit 1a may take place on more than 1 day (e.g., MRI scan occurs on separate day). Subjects cleared for continued participation will undergo the following procedures at the second screening (**1b**). The tasks below may be performed on the same day, or may be performed on separate days. Screening 1b will occur within one calendar month of screening 1a.

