## **Screening Visit 1b:**

- Blood work
  - Inflammatory biomarkers
  - Metabolomics
  - Primary Panel for Inflammation, Oxidative, and Nitrosative Stress
  - APOE status (if unknown)
- Retinal Imaging
- If the subject has had a clinic or research LP within 6 months prior to visit 1b and CSF has been banked, no screening LP will be performed. The banked CSF will be used for analysis. In all other cases, an LP will be performed by an MD or NP following an overnight (no less than 6-hr) fast. CSF will be assessed for the following:

- Aβ42, tau, phospho tau
- Inflammatory Biomarkers
- Contact subject on the day after LP to inquire about any adverse events.

8.3 Baseline Visits. The baseline visit will occur within 1 calendar month of Screening visit1b. Patients that continue to meet eligibility requirements will undergo the following at visit2a.

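### Some subjects given flicker at screening visit 1a can leave before any scheduled adverse event assessment, with no stated place in the safety results

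*Combined protocol and SAP*

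**What the plan says.** Section 2.1 (Aim 1) promises: "In addition, we will closely monitor the safety of this procedure and document the occurrence of any adverse events". It sets no start date and names no population. Section 4.1 adds: "The primary goals are to measure safety and FLICKER tolerance while verifying the intended response".

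The visit 1a list in section 8.2 includes "Flicker Tolerance Testing" and, under EEG, "Flicker entrainment and exposure titration". Section 10.2 confirms that the device is in use during EEG recording. It has entrainment judged at 1a and 2b, and states: "If subjects' brain waves are unable to become entrained, they will be removed from the study". A repeat screening EEG is allowed for subjects who meet every other entry criterion.

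Only subjects cleared after 1a go on to 1b, and "Screening 1b will occur within one calendar month of screening 1a". Section 8.3 allows up to one further calendar month from 1b to baseline. At 1b the instruction is "Contact subject on the day after LP to inquire about any adverse events". For a subject with a clinic or research puncture in the preceding six months whose "CSF has been banked, no screening LP will be performed", there is no puncture for that contact to follow.

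The first visit list with an adverse event review is 2b, where randomisation also takes place. Section 9.1 requires an electronic case report form for every consented patient. The Statistical Analysis section defines no safety population for anyone.

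**The concern.** Safety and tolerance are primary goals, and reactions at first exposure belong to both, including those of people who do not continue. The protocol itself treats some reactions as possible: section 7.3 excludes epilepsy and migraine because flicker may worsen them, and it excludes drugs that lower the seizure threshold.

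If subjects can be exposed, react, and leave before anyone is scheduled to ask, a summary built on the randomised group would describe people selected after their first exposure. The Statistical Analysis section intends the data for preparing a larger trial, so the selection would carry over into that trial's planning.

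**Working it through.** The plan has no figure of its own to reproduce. The check has two parts: the schedule, and an illustration of scale.

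**Schedule.** Reading the rows of the two tables in section 8.8 against the visit columns:

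- Adverse event assessment, Table 1: 2b, 3, 4, 5, 6a, 7 to 10, 11a.
- Adverse event assessment, Table 2: 2b, 3, 4, 5, 6, 7a, 8 to 10, 11a.
- Neither row is marked at 1a, 1b or 2a. The 1a visit list agrees, having no adverse event item.
- The telephone row in both tables starts at visit 3, so the contact after the 1b puncture appears in neither table.
- Tolerance testing is marked at 1a in both tables.

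For a subject given flicker at 1a, the scheduled enquiry depends on when the subject is removed:

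| Point of removal | Scheduled adverse event enquiry by then |
|---|---|
| After 1a, before 1b | None |
| After 1b, banked CSF used | None |
| After 1b, lumbar puncture done | Contact the day after the puncture |
| At 2b | The 2b review (listed before that day's EEG) |

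The gap is the first two rows. A non-entrainer falls in the first row if removed straight after 1a. One kept for a repeat EEG has met the other criteria, so will usually have had the contact after the puncture.

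**Scale, illustration only.** The documents give no screen-failure rate. Assume N people exposed at 1a, 10 randomised (section 4.1), and all the others gone before 2b. The share that could lack a scheduled enquiry is at most (N − 10)/N:

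- N = 12: 2/12 = 16.7%
- N = 15: 5/15 = 33.3%
- N = 20: 10/20 = 50.0%

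These are upper bounds, because the contact after the puncture reaches some of those who leave.

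For the effect on a reported rate, use exact (Clopper-Pearson) two-sided 95% limits. With 0 events in n people the upper limit is 1 − 0.025^(1/n): 30.8% for n = 10, 26.5% for 12, 21.8% for 15 and 16.8% for 20. A clean result in all exposed people would therefore be more informative than one in the 10 randomised.

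At the other extreme, suppose none of the 10 randomised has an event and everyone who left did. The report on the 10 is 0/10 (95% CI 0 to 30.8%). Over all exposed it is 2/12 = 16.7% (2.1% to 48.4%) with two leavers, or 5/15 = 33.3% (11.8% to 61.6%) with five.

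**The case against.** The best defence is that much is already captured. First exposure is on site, tolerance testing is a scheduled item at 1a, Aim 1 covers any adverse event, every consented patient has a case report form, and section 6.1 has investigators reviewing data from study visits. A blank table cell is also weak evidence here: vital signs are in the midpoint and end-of-study visit lists but unmarked at those visits in both tables.

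Part of this stands. Removed subjects do have a record, and an event seen at 1a would probably be noted. But the text reviewed does not say what tolerance testing records, and the case report forms hold what the protocol asks for, which at 1a does not include adverse events. The blank cells at 1a also agree with the 1a visit list, unlike those for vital signs.

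A reader might infer three stronger things that the documents do not support.

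- That nobody is asked before 2b. A screening lumbar puncture is the default, and the contact after it is an adverse event enquiry.
- That every retained subject may wait about two months for a first enquiry. That needs banked CSF. With a puncture, the contact comes the day after it, about a month from 1a at most if the puncture is on schedule. Even the two-month span is not a firm cap, since visits may extend over several days.
- That the plan excludes removed subjects from the results. It is silent about them, as it is about analysis populations generally.

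**Conclusion.** The point holds in limited form. Subjects given flicker at 1a and removed before 1b, or removed after 1b with banked CSF in place of a puncture, have no scheduled adverse event assessment before they leave. Exposed but non-randomised subjects have no stated place in the safety results in the text reviewed. The part of the protocol between sections 4 and 6 was not available, and nothing is claimed about it.

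The possible bias is towards a more favourable picture of first-exposure safety. Its size cannot be taken from the documents: the counts of 12, 15 and 20 exposed and the event patterns are assumptions. Removing non-entrainers is a legitimate entry choice and is not the fault here. The gap touches a primary goal and should be closed, but it does not invalidate the pilot.

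**What to change.** Leave the removal rule and entry procedures as they are, and make three changes.

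1. Mark adverse event assessment at 1a, after flicker, and at 1b, in both visit lists and in Tables 1 and 2. At 1b this also covers subjects with banked CSF, who still attend for blood work and retinal imaging. Enter the existing contact after the puncture in the tables.
2. Ask about adverse events whenever a flicker-exposed subject is removed before 2b. An entry at 1a alone would miss reactions that appear after the visit.
3. State that safety will be reported for all flicker-exposed subjects, alongside the randomised group.

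Optionally, also report the number tested and the number removed for non-entrainment, without counting non-entrainment as intolerance. This would help plan the larger trial, but the point does not depend on it.

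The cost is a few extra form entries and enquiries at existing contacts. The case report form for every consented patient already gives the data a place. The safety summary may be less favourable.
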